To evaluate the preliminary safety and tolerability of BMS-986249 in combination with nivolumab (Arm C and Arm F) relative to ipilimumab in combination with nivolumab (Arm D) in participants with previously untreated, unresectable or metastatic melanoma	• Incidence of treatment-related Grade 3-5 AEs within 24 weeks
To evaluate the preliminary efficacy of BMS- 986249 in combination with nivolumab (Arm C and Arm F) relative to historic nivolumab monotherapy data in participants with previously untreated, unresectable or metastatic melanoma	ORR as assessed by investigator using RECIST v1.1
Secondary	
To assess the anti-tumor activity of BMS-986249 in combination with nivolumab (Arm C and Arm F) and ipilimumab in combination with nivolumab (Arm D) in participants with previously untreated, unresectable or metastatic melanoma	ORR, DOR, PFS, and TTR as assessed by investigator using RECIST v1.1
To assess the safety and tolerability of BMS- 986249 in combination with nivolumab (Arm C and Arm F), and ipilimumab in combination with nivolumab (Arm D) in participants with previously untreated, unresectable or metastatic melanoma	Incidence of AEs, SAEs, AEs leading to discontinuation, death, and laboratory abnormalities
To characterize the PK of BMS-986249 when administered in combination with nivolumab	 Summary measures of PK parameters of BMS-986249 in combination with nivolumab
To evaluate time to deterioration (TTD) in Quality of Life (QoL) and physical functioning	• TTD as defined by a minimally important decrease from baseline ≥10 points on the EORTC QLQ-C30 global health status/quality of life subscale (items 29 & 30) and Physical Functioning Scale (items 1 to 5)
Exploratory	
To explore the associations between PK of BMS-986249, ipilimumab and nivolumab, safety, efficacy, and clinical biomarkers such as, but not limited to T cell-specific genes	Association measures between BMS986249, ipilimumab, and nivolumab PK levels, select outcomes, and biomarkers of interest
BMS-986249, ipilimumab and nivolumab, safety, efficacy, and clinical biomarkers such as, but not	ipilimumab, and nivolumab PK levels, select

Protocol Amendment No.: 09

Date: 14-Mar-2023 78

Table 4-2: Objectives and Endpoints: The Dose Expansion Phase in Melanoma (Part 2A)

Objectives	Endpoints	
To characterize the immunogenicity of BMS-986249, ipilimumab and nivolumab	Incidence of ADA to ipilimumab, nivolumab, and BMS-986249	

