- Arm A: 240 mg BMS-986249 in combination with 360 mg nivolumab administered IV Q3W for 4 doses (Combination Therapy Phase) as a co-administration, followed by 480 mg nivolumab monotherapy administered IV over approximately 30 minutes Q4W (Maintenance Phase), which will begin 3 weeks after the last combination dose.
- Arm B: 800 mg BMS-986249 administered IV Q8W in combination with 480 mg nivolumab administered IV Q4W. Co-administration will continue on cycles where both study treatments are scheduled, while nivolumab will be administered IV over approximately 30 minutes when scheduled as a monotherapy.
- Arm C: 1,200 mg BMS-986249 administered IV Q8W in combination with 480 mg nivolumab administered IV Q4W. Co-administration will continue on cycles where both study treatments are scheduled, while nivolumab will be administered IV over approximately 30 minutes when scheduled as a monotherapy.
- Arm D: 3 mg/kg ipilimumab in combination with 1 mg/kg nivolumab administered IV Q3W for 4 doses (Combination Therapy Phase), followed by 480 mg nivolumab monotherapy administered IV over approximately 30 minutes Q4W (Maintenance Phase), which will begin 3 weeks after the last combination dose. Nivolumab and ipilimumab will be administered sequentially as 2 separate IV infusions. Nivolumab will be given first, over approximately 30 minutes, followed by ipilimumab over approximately 30 minutes, beginning approximately 30 minutes after completion of the infusion of nivolumab.
- Arm E: 480 mg nivolumab monotherapy administered IV over approximately 30 minutes Q4W.
- Addendum Per Revised Protocol 07: Part 2A Arm A, Arm B, and Arm E are discontinued for further enrollment/randomization. The modification of enrollment/randomization in Part 2A is not a consequence of changes in the safety or tolerability profile or benefit/risk assessment of BMS-986249 (see Section 5.5.4). Currently active participants in these arms will continue treatment as assigned and may remain on treatment until protocol-defined discontinuation criteria have been met. In accordance with Revised Protocol 07, participants in Part 2A will be randomized across the study approximately 1:1:1 between 3 treatment arms:
 - Arm C: described above
 - Arm D: described above
 - Arm F: 600 mg BMS-986249 administered IV Q4W in combination with 480 mg nivolumab administered IV Q4W as a co-administration.

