5.1.2.4 The BMS-986249 Cohort Expansion Combination Therapy (Part 2)

The purpose of the cohort expansions is to gather preliminary efficacy information in specific populations regarding BMS-986249 in combination with nivolumab. In addition, safety, tolerability, PK, and information will be evaluated. Further, patient-reported quality of life, symptoms, and treatment tolerability will be assessed using the EORTC QLQ-C30, EQ-5D-3L, FACIT GP5, and PRO-CTCAE (see Section 9.9).

The BMS-986249 in Combination with Nivolumab Randomized Cohort Expansion in Melanoma (Part 2A) will evaluate the efficacy and safety of BMS-986249 in combination with nivolumab relative to ipilimumab combined with nivolumab, and historical nivolumab monotherapy data, in a cohort of participants with previously untreated, unresectable or metastatic melanoma. See Section 5.1 and Figure 5.1-2.

The BMS-986249 in Combination with Nivolumab Additional Tumor Cohort Expansion (Part 2B) will evaluate the safety and tolerability of BMS-986249 in combination with nivolumab through single-arm expansion cohorts in previously treated advanced or intermediate HCC, metastatic CRPC, and unresectable locally advanced or metastatic TNBC.

Preliminary reviews of the data in Part 1 and Part 2 will occur prior to the final data base lock, in order to assess the initial safety, PK, and signal. The earliest assessment of the efficacy signal for a Part 2A arm and/or Part 2B tumor cohort may be performed after approximately 15 to 20 participants are randomized into the arm/cohort and complete the first tumor scan (at about 8 to 12 weeks after start of treatment). The evaluation of this preliminary data will assist in further planning for the study, including the option to discontinue treatment arm(s) or de-escalate individual Part 2 arm/cohort dose levels, if supported by the data. The study is expected to continue as planned during this evaluation, until the interpretation of the data is complete. Any changes to the design based on such evaluation may be implemented via a protocol amendment, unless already anticipated and planned for by the current protocol.

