5.4.7.1 Rationale for Ipilimumab and Nivolumab Combination Therapy as a Reference

The combination of ipilimumab and nivolumab has been approved in the US, European Union, Australia, and additional regions for the treatment of metastatic melanoma. In study CA209067, 3 mg/kg ipilimumab in combination with 1 mg/kg nivolumab demonstrated a response rate of 58%, numerically higher than either single agent. In trial CA209069, the same combination dose achieved a response rate of 61%, significantly greater than that of ipilimumab alone. While the efficacy of the combination was improved, the incidence of serious adverse reactions, adverse reactions leading to permanent discontinuation or dosing delays, any grade drug-related select AEs, and Grade 3-4 AEs was higher in the combination arm of each study than in the respective monotherapy arms (see Table 5.4.7.1-1).^{24,25}

to discontinuation

Nivolumab in **Combination with Safety Result** Nivolumab (N=313) Ipilimumab (N=311) Ipilimumab Regimen (N=313)299 (95.5%) TRAEs - Any grade 257 (82.1%) 268 (86.2%) TRAEs - Grade 3-4 51 (16.3%) 172 (55.0%) 85 (27.3%) Drug-related select AEs -25 (8.0%) 150 (47.9%) 69 (22.2%) Any grade Drug-related select AEs -18 (5.8%) 112 (35.8%) 51 (16.4%) Grade 3-4 Drug-related AEs leading 24 (7.7%) 114 (36.4%) 46 (14.8%)

Table 5.4.7.1-1: CA209067 Safety Result Summary

Abbreviations: AE = adverse event; TRAE = treatment-related adverse event.

The combination of ipilimumab and nivolumab (Arm D) was chosen as a reference arm in Part 2A because the combination contains the parental antibody (ipilimumab) of BMS-986249. As an anti-CTLA-4 Probody, BMS-986249 is hypothesized to have preferential activity in the tumor microenvironment relative to normal tissue. BMS-986249 may then result in a reduction of the systemic irAEs seen after treatment with ipilimumab in combination with nivolumab, while maintaining anti-tumor activity. Including ipilimumab in combination with nivolumab will therefore allow for a more complete assessment of the therapeutic index of BMS-986249 in combination with nivolumab.

The dose and schedule of 3 mg/kg ipilimumab in combination with 1 mg/kg nivolumab administered IV Q3W for 4 doses (Combination Therapy Phase), followed by 480 mg nivolumab monotherapy administered IV Q4W (Maintenance Phase), beginning 3 weeks after the last combination dose, is based on the approved recommended dose in advanced melanoma.²⁶

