PFS PFS for a participant is defined as the time from the first dosing date (Part 1, Part 2B) or randomization date (Part 2A) to the date of first objectively documented disease progression per RECIST v1.1 or PCWG3 or death due to any cause, whichever occurs first.	Median and CI by K-M method and PFS rates
PSA Response Rate (For Part 2B CRPC Participants Only) Decrease in the level of PSA of at least 50% from baseline maintained for at least 3 weeks	Point estimate and CI
TTR TTR is defined as the time from the first dosing date (Part 1, Part 2B) or randomization date (Part 2A) to the date of the first confirmed response (CR or PR) per RECIST v1.1 or PCWG3.	Summary statistics for TTR
OS OS is defined as the time from enrollment (Part1, Part 2B) or randomization (Part 2A) to the date of death from any cause	Median and CI by K-M method (including OS rates, for example at 1 year and 2 years)

Abbreviations: BOR = best overall response; CI = confidence interval; CR = complete response; DOR = duration of response; K-M = Kaplan Meier; ORR = Objective Response Rate; OS = overall survival; PCWG3 = Prostate Cancer Working Group 3; PFS = progression-free survival; PR = partial response; PSA = prostate-specific antigen; RECIST = Response Evaluation Criteria in Solid Tumors; TTR = time to response.

Protocol Amendment No.: 09

^a Efficacy analyses will be executed with a 60% two-sided CI.

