10.3.7 Patient-Reported Outcome Analyses

PRO analyses are described in Table 10.3.7-1.

Table 10.3.7-1: PRO - Statistical Analyses

[figure not shown]
Secondary Endpoint	Statistical Analysis Methods
To evaluate TTD in Global Health Status/QoL of the EORTC QLQ-C30 (Part 2A only)	TTD in Global Health Status/QoL and Physical Functioning will be defined as the time from randomization until a clinically meaningful decline (ie, reduction ≥10 points) from baseline in EORTC QLQ-C30 global health/quality of life subscale score and Physical Functioning Scale score. Estimates for both Global Health Status/QoL and Physical Functioning will be provided with associated 95% CIs.
To evaluate TTD in Physical Functioning Scale of the EORTC QLQ-C30 (Part 2A only)	The analysis will use all available data from randomized participants, including data collected during post-treatment follow up. Median deterioration times, hazard ratios, and 95% CIs will be calculated

Abbreviations: CI = confidence interval; EORTC = European Organisation for Research and Treatment of Cancer; PRO = patient-reported outcome; QLQ-C30 = Quality of Life Questionnaire – Core 30; QoL = quality of life; TTD = time to deterioration.

Analyses of PRO will be performed on participants who have an assessment at baseline and at least 1 post-baseline assessment.

Further exploratory analyses for Part 2A and Part 2B not specified here will be described in the Statistical Analysis Plan, which will be finalized before database lock and may be presented separately from the main clinical study report.

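### Part 2A prespecifies no between-arm PFS contrast, although Arms C, D and F are randomised and efficacy is to be judged against ipilimumab plus nivolumab

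*Combined protocol and SAP*

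**What the plan says.** **Design.** Under the Revised Protocol 07 addendum in Section 5.1, "participants in Part 2A will be randomized across the study approximately 1:1:1 between 3 treatment arms": C, D and F. Randomisation is stratified by PD-L1 status and M-stage (Sections 5.1 and 5.4.8).

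**Purpose.** Section 5.1.2.4 says Part 2A "will evaluate the efficacy and safety of BMS-986249 in combination with nivolumab relative to ipilimumab combined with nivolumab", and also relative to historical nivolumab data. Section 5.4.7.1 gives the reason for Arm D: BMS-986249 is hypothesised to reduce immune-related toxicity while keeping anti-tumour activity, so the arm will "allow for a more complete assessment of the therapeutic index of BMS-986249 in combination with nivolumab".

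**PFS analysis.** PFS is a secondary endpoint, timed from "randomization date (Part 2A) to the date of first objectively documented disease progression" or death. Part 2A efficacy is analysed in the randomised population (Section 10.3.1). The method column for PFS reads "Median and CI by K-M method and PFS rates", and footnote a of the table sets two-sided 60% intervals. No landmark time is named for the PFS rates.

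**Other endpoints.**
- The primary safety estimand (Table 4-4) names C vs D and F vs D.
- ORR in Part 2A has a chi-square test, a stratified Cochran-Mantel-Haenszel odds ratio with 60% interval, and adjusted and unadjusted differences (Tables 4-4 and 10.3.1-1). The arm pairs are not named.
- For QLQ-C30 time to deterioration, Table 10.3.7-1 states that "Median deterioration times, hazard ratios, and 95% CIs will be calculated".

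**The concern.** A tolerability gain over Arm D is worth having only if disease control is kept. The toxicity side of that trade-off is a named randomised comparison. The primary efficacy objective is set "relative to historic nivolumab monotherapy data", and Section 5.4.7 itself warns that historical controls may not represent current patients. Response rate says nothing about durability, and duration of response exists only in responders, so it is not a randomised comparison. PFS is the measure left.

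With per-arm summaries only, the reader must compare medians or rates by eye. That sets aside the stratification and most of each curve, and it yields no single estimate of the PFS difference with its uncertainty. The plan does not avoid hazard ratios on principle, since it uses them for a patient-reported endpoint.

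**Working it through.** **No PFS figure to reproduce.** The plan states no PFS event count or power. Its 60 per arm with about 70% power concerns 24-week Grade 3-5 treatment-related events. The proportions are redacted, so that figure can only be checked for plausibility. With the 55% Grade 3-4 rate for the combination in Table 5.4.7.1-1 as control, one-sided 0.10 and 60 per arm, 70% power corresponds to 38.6% on treatment, a ratio of 0.70.

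**Inputs for PFS.**
- From the documents: 60 per arm; minimum follow-up of 36 weeks at final analysis (Section 10.1.2.2), which is 36 × 7 / 30.44 = 8.28 months; two-sided 60% intervals, so z = 0.8416, the one-sided 20% level.
- Assumed, because the documents give no melanoma PFS: exponential PFS; Arm D median m of 8, 11 or 14 months; uniform accrual over A = 12 or 24 months; a true loss of HR 1.5; administrative censoring only.

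**Contrast using the whole curve.**
- With rate λ = ln 2 / m in Arm D and 1.5λ in the comparator, the chance of an observed event is 1 − [exp(−8.28λ) − exp(−λ(8.28 + A))] / (λA).
- Power is Φ(ln 1.5 × √events / 2 − 0.8416).
- Fewest events (m = 14, A = 12): 60 × (0.500 + 0.642) = 68.5; Φ(1.678 − 0.842) = 80%.
- Most events (m = 8, A = 24): 60 × (0.795 + 0.896) = 101.4; Φ(2.042 − 0.842) = 88%.

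**Informal difference in K-M rates at 36 weeks.** Everyone is followed that long, so each rate is a simple proportion. With S_D = exp(−8.28λ) and S_C = S_D^1.5, power is Φ(d/SE − 0.8416).

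| Arm D median | S_D | S_C | d | SE | Rate difference | Whole curve (12 / 24 months' accrual) |
|---|---|---|---|---|---|---|
| 8 | 0.488 | 0.341 | 0.147 | 0.089 | 79% | 86% / 88% |
| 11 | 0.594 | 0.457 | 0.136 | 0.090 | 75% | 83% / 86% |
| 14 | 0.664 | 0.541 | 0.123 | 0.089 | 71% | 80% / 84% |

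Simulation agrees: 80-88% for the log-rank test and 70-81% for the 36-week difference, both at about 20% error. The gain is about 7 to 14 points. With a 6-month landmark, the rate difference has 63-76%.

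**Non-overlap of the 60% intervals for the medians.** Simulated power is 59-62%, at an error of about 9-12%. At a matched 11% and 79 events, the log-rank approximation gives ln 1.5 × √79 / 2 − 1.23 = 0.57, or about 72%, so roughly 10 points of that gap remain. With m = 14 and 12 months' accrual, the Arm D median is not reached in about 11% of trials and its upper limit in about 32%. A hazard ratio stays estimable.

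**Precision of the added estimate.** The 60% interval factor is exp(2 × 0.8416 / √events): 1.24 at 60 events and 1.18 at 101. At one-sided 10% and 60 events, power for HR 1.5 is only about 61%.

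**The case against.** **The wording is descriptive.** The secondary objective is "To assess the anti-tumor activity of BMS-986249 in combination with nivolumab (Arm C and Arm F) and ipilimumab in combination with nivolumab (Arm D"), joined by an and, whereas both primary objectives are comparative. Section 10.1.2.2 calls the design exploratory proof of concept. This stands, and it is why the added quantities should be estimates without a claim. It does not cancel the comparative aim in Sections 5.1.2.4 and 5.4.7.1.

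**The SAP may supply it.** Section 10.3 is a summary, and Section 10.3.1 leaves further time-to-event detail to an SAP whose text is not in these documents. A reader might infer that the arms will never be contrasted on PFS. The documents support only that no such contrast is prespecified. What is deferred, however, is detail of the calculation; the method entry is already filled in without a contrast.

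**ORR covers efficacy.** A reader might infer that a loss of efficacy against Arm D would easily be missed. The ORR analyses do not support that: a fall from 59% to 45% (the combination and nivolumab rates in Table 5.4.7.2-1) has about 76% power at one-sided 20% with 60 per arm. The gap is confined to PFS.

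**Nobody plans to compare median intervals by overlap.** Correct. Because the plan also reports PFS rates, the fairer comparator is the 36-week difference.

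**A hazard ratio would not be clean.** Arm F opened with Revised Protocol 07, when Arm D was already randomising (Sections 5.1 and 7.2), so an unrestricted F vs D contrast mixes in non-concurrent controls. Censoring can also differ by arm. PFS is censored at subsequent therapy (Section 10.3.1), and imaging ends 100 days after end of treatment (Section 5.1.5.2). Arm D participants who miss combination cycles go to follow-up, while those in C or F may continue nivolumab alone (Section 8.1). Both points stand and shape the fix. By-eye comparison of medians and rates inherits the same problems.

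**Conclusion.** The concern holds in a limited form. The protocol prespecifies no between-arm PFS contrast for Part 2A, although the design supports one and the stated purpose calls for one.

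Under the assumptions above, a randomised contrast at the plan's own confidence level gains about 7 to 14 points of power over an informal 36-week rate difference. It also provides an estimate with an interval, a factor of about 1.2 either way. A reader might take the 59-62% for median non-overlap as the plan's power; it is not, because no such rule is planned and much of that shortfall comes from its lower error rate.

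The power figures are likely to be optimistic. They ignore censoring at subsequent therapy and the 100-day imaging limit, and Section 10.3 describes a final analysis only about 6 months after the last participant's first visit. What is missing is an estimate with its interval rather than a decisive test. This is a cheap improvement.

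**What to change.** In the PFS row of Table 10.3.1-1, keep the K-M medians and rates by arm. For Part 2A, add as descriptive estimates:

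- Hazard ratios for Arm C vs Arm D and Arm F vs Arm D with two-sided 60% intervals, from a Cox model stratified by PD-L1 status and M-stage in the randomised population.
- The difference in K-M PFS rate at one prespecified landmark, with 60% interval.
- For F vs D, only Arm D participants randomised concurrently with Arm F, after Revised Protocol 07. The loss should be small. Section 5.2 puts up to about 20 participants in Arms A, B and E together before that revision, so equal allocation implies about 20 / 3 ≈ 7 in Arm D.
- A sensitivity analysis that does not censor at subsequent anti-cancer therapy. Section 5.1.5.2 ends imaging at that point, so the SAP should say which later events are used, or whether starting new therapy counts as an event.

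The cost is wording and one table, with no new data, visits or participants. It can still be prespecified, because Section 10.3 has the SAP signed before database lock. The downside is a few more estimates without multiplicity control, consistent with the stated proof-of-concept approach.

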2 SCHEDULE OF ACTIVITIES

Study assessments and procedures are shown in Table 2-1, Table 2-2, Table 2-3, Table 2-4, and Table 2-5.

In limited instances, scheduled events (including events other than safety assessments) can occur outside of the indicated timeframes but the Sponsor should first be notified.

If a participant has a delay in study treatment administration for any reason, then assessments and laboratory tests (with the exception of any tests needed to ensure participant safety) should be correspondingly delayed with the exception of tumor assessments. Tumor assessments continue per protocol schedule regardless of any treatment delay incurred.

The pharmacokinetic (PK), and safety profiles of BMS-986249 are being elucidated, modifications to the procedures (ie, reduction in PK, sampling, timing of procedures, dose schedules) currently outlined in Section 2 and Section 9 may be required. These modifications will not include the addition of new procedures and will be documented in a note to file or administrative letter.

In the event that multiple procedures are required at a single time point, the electrocardiogram (ECG) may be obtained up to 15 minutes earlier, vital signs may be obtained up to 10 minutes earlier or later, and clinical laboratory samples may be obtained up to 5 minutes earlier than the nominal time point, ensuring the PK samples can be collected on time.

 Table 2-1:
 Screening Schedule of Activities for All Study Parts

Procedure	Screening Visit (Days -30 to -1)	Notes					
Eligibility Assessments							
Informed Consent	X	Must be obtained prior to performing any screening procedures. A participant is considered enrolled only when a protocol-specific ICF is signed.					
Contact IRT	X	After the participants meet all eligibility criteria, sites will use IRT for participant number assignment. Register in IRT to obtain participant number. Subsequent visits will be registered into the IRT system for drug supply. See Section 5.1.1. If the IRT system is not available, participants will be enrolled manually. The participant number will be created in the IRT system upon availability.					
Inclusion/Exclusion Criteria	X	Must be confirmed prior to randomization/treatment assignment. See Section 6.1 and Section 6.2.					
Medical History	X	All medical history relevant to the disease under study. Include any toxicities or allergies related to previous treatments.					
Prior Cancer Therapies	X						

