5.1.1 Screening Period

The screening period will be up to 30 days and begins by establishing the participant's initial eligibility and signing of the informed consent form (ICF). The screening assessments are shown in Table 2-1. If a participant exceeds the 30-day screening period due to a study-related procedure (eg, scheduling of a tumor biopsy or waiting for a study-related laboratory value), the participant must be re-consented and will require a new participant identification number. In this situation, the fewest number of procedures from the initial screening should be repeated to qualify the participant, while maintaining participant safety and eligibility. For Part 2A participants awaiting PD-L1 results, the screening window may be extended past the 30-day period upon discussion with the Medical Monitor (or designee). However, if screening extends over a prolonged period, baseline procedures, such as tumor assessments and labs, may need to be repeated so that they fall within the acceptable protocol-specified window. Within a given disease type, participants meeting all eligibility criteria will be enrolled in the study according to the part and treatment arm availability.

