10.2 Populations for Analyses

For purposes of analysis, the populations are defined in Table 10.2-1.

Table 10.2-1: Populations for Analyses

Population	Description		
Enrolled	All participants who sign informed consent		
Randomized	All participants who are randomized to treatment arm (Part 2A)		
Treated	All participants who take at least 1 dose of study treatment		
Pharmacokinetic	All treated participants who have evaluable concentration-time data		
Immunogenicity	All treated participants who have baseline and at least 1 post-baseline pre-infusion immunogenicity assessment for the analyte evaluated		

Protocol Amendment No.: 09

Table 10.2-1: Populations for Analyses

Population	Description
Biomarker	All treated participants with available biomarker data.
Patient-reported outcome	All treated participants with patient-reported outcome data at baseline and at least 1 post-baseline assessment.

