10.3.1 Analyses

The Part 2A efficacy analyses will be performed on the randomized population, with supplemental analyses on the treated population, while the efficacy analysis of Part 2B will be performed on the treated population (Table 10.3.1-1). The efficacy and safety analysis for Part 2B will be evaluated by tumor-specific cohort. Analysis of the treated participants from Part 1 will be presented separately. The following censoring rules will be applied for the definition of PFS and DoR:

- Subjects who did not progress or die will be censored on the date of their last evaluable tumor assessment.
- Subjects who did not have any evaluable on study tumor assessments and did not die will be censored on their date of randomization (for Part 2A) or first dosing (Part 1 and Part 2B).
- Subjects who receive subsequent anti-cancer therapy prior to documented progression or death will be censored at the date of the last evaluable tumor assessment conducted on or prior to the date of initiation of the subsequent anti-cancer therapy.

Additional details of the calculation of time-to-event endpoints such as DOR and PFS will be described in the Statistical Analysis Plan.

The efficacy and safety data from participants randomized in Part 2A Arms A, B, and E before Revised Protocol 07 will be analyzed using descriptive measures only.

Table 10.3.1-1: Efficacy - Statistical Analyses^a

Endpoint	Statistical Analysis Methods
Best observed response (BOR) BOR for a participant will be assessed per RECIST v1.1 or PCWG3 by investigator, unless otherwise specified	Summary and listing of BOR

Protocol Amendment No.: 09

Table 10.3.1-1: Efficacy - Statistical Analyses^a

Endpoint	Statistical Analysis Methods
ORR ORR is defined as the proportion of participants whose BOR is either CR or PR per RECIST v1.1 in the population of interest or PCWG3 for participants with prostate cancer.	Point estimate and CI by arm/cohort in Parts 2A and 2B Part 2A: Chi square test and sensitivity analysis using Cochran-Mantel-Haenszel test with the stratification factors as strata
DOR DOR for a participant with a BOR of CR or PR is defined as the time between the date of first response and the date of the first objectively documented tumor progression per RECIST v1.1 or PCWG3 or death, whichever occurs first.	Median and CI by K-M method for participants who responded, by arm/cohort

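### OS in Part 1 and Part 2B starts at enrollment, defined as consent, although these parts are analysed in treated participants and PFS and TTR start at first dose

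*Combined protocol and SAP*

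**What the plan says.** On the OS clock, Section 10.3.1 (Table 10.3.1-1) reads: "OS is defined as the time from enrollment (Part1, Part 2B) or randomization (Part 2A) to the date of death from any cause". The protocol explains enrollment in two places. The informed-consent row of Table 2-1 says: "A participant is considered enrolled only when a protocol-specific ICF is signed". Table 10.2-1 defines the enrolled population as "All participants who sign informed consent".

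On the analysis set, Section 10.3.1 says that "the efficacy analysis of Part 2B will be performed on the treated population", and it presents Part 1 separately, also in treated participants. Table 10.2-1 defines treated as having received at least one dose.

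On the neighbouring endpoints, the same table says "PFS for a participant is defined as the time from the first dosing date (Part 1, Part 2B) or randomization date (Part 2A"), and likewise "TTR is defined as the time from the first dosing date (Part 1, Part 2B) or randomization date (Part 2A").

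On the length of the gap, Section 5.1.1 limits screening to 30 days. If a study-related procedure takes a participant past that limit, "the participant must be re-consented and will require a new participant identification number". The only extension it allows is for Part 2A participants waiting for PD-L1 results.

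On follow-up, Tables 4-2 and 4-3 list OS rates at 1 and 2 years as exploratory endpoints for Parts 2A and 2B. Table 10.3.1-1 gives a Kaplan-Meier median with the same landmarks as examples. The Amendment 09 addendum in Section 5.1.5.3 ends survival follow-up 100 days after EOT, takes participants already beyond that point off study, and gives as its reason that no more formal OS analysis is planned. Section 10.3.1 lists censoring rules for PFS and DOR but none for OS.

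**The concern.** Membership of the treated population is decided at first dose, but the OS clock starts before it. Anyone who died between consent and first dose is by definition not in the analysis. The interval is therefore death-free for everyone who is counted, and it can only lengthen OS relative to OS from first dose.

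It also puts two clocks in one table. A Part 2B participant who dies without progression has a PFS time and an OS time that end on the same day but differ in length. The Part 2B cohorts are single-arm, so no concurrent control carries the same shift, and any reading of OS against outside figures takes the shift with it.

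Separately, once follow-up is tied to EOT, when a participant leaves the OS risk set can depend on when treatment stopped. Stopping is often related to prognosis, so censoring may be informative.

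**Working it through.** The plan states no OS sample size, event count or target precision, so there is no figure of its own to reproduce. The check compares definitions and then sizes the shift.

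**Definitions.** OS origin: enrollment, meaning consent (Tables 10.3.1-1, 2-1 and 10.2-1). Analysis set: at least one dose (Section 10.3.1, Table 10.2-1). PFS and TTR origin: first dose. Let g be the time from consent to first dose. Every treated participant's OS is the time from first dose to death, plus g.

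**Size of g.** The nominal maximum is 30 days (Section 5.1.1), because a longer screening leads to a new consent and a new participant number. The documents give no distribution of g. I use 10 and 30 days: 10/30.44 = 0.329 months and 30/30.44 = 0.986 months.

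**Median.** It is later by exactly g, that is 0.33 to 0.99 months. Against the medians below this is 0.33/11.2 = 3% to 0.99/9.95 = 10%.

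**Landmark rates.** If S is survival from first dose, the rate reported at time t is S(t − g), so the shift is S(t − g) − S(t). I assume exponential survival, S(t) = 2^(−t/m). For m I take three median OS values that Section 5.4.9 cites from earlier studies: 9.95 and 11.2 months (CRPC, placebo and ipilimumab arms, both with radiotherapy) and 10.6 months (TNBC, nivolumab with ipilimumab).

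Example, m = 9.95, t = 12, g = 0.986: S(12) = 2^(−1.206) = 0.434; S(11.014) = 2^(−1.107) = 0.464; shift = +3.1 points.

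| m (months) | 1 year, 10 days | 1 year, 30 days | 2 years, 10 days | 2 years, 30 days |
|---|---|---|---|---|
| 9.95 | +1.0 | +3.1 | +0.4 | +1.3 |
| 10.6 | +1.0 | +3.0 | +0.5 | +1.4 |
| 11.2 | +1.0 | +3.0 | +0.5 | +1.4 |

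Entries are percentage points.

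**Follow-up.** Counting from first dose, a participant followed only to EOT + 100 days is still at risk at 1 year if EOT falls on or after day 365 − 100 = 265, and at 2 years if it falls on or after day 730 − 100 = 630. On a consent clock with a 30-day gap these become days 235 and 600. This shows how the risk set depends on EOT. It does not give the size or the sign of any bias.

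**The case against.** **Enrollment is used in a second sense.** Section 5.1.1 also says that "participants meeting all eligibility criteria will be enrolled in the study according to the part and treatment arm availability", which places enrollment after eligibility is established. This stands as a reason to treat 30 days as an upper limit. It does not remove the point: that date still precedes first dose, the two explicit definitions both say consent, and two meanings are themselves a reason to name the date.

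**The effect is small against the noise.** Table 10.3.1-1 uses 60% intervals. For 40 participants with S = 0.434 and no censoring, the half-width is 0.842 × √(0.434 × 0.566/40) = 6.6 points, so a shift of 3.1 points is under half of it. That is fair, and it supports a minor rating. But the shift is systematic, in one direction, and avoidable at almost no cost.

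**The borrowed medians come from other regimens, and none is for HCC.** True. They indicate scale only.

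**The SAP can settle it.** Section 10.3.1 leaves further time-to-event detail to the SAP, naming DOR and PFS. The OS origin, however, is already fixed in the table. A SAP that follows it inherits the mismatch, and one that departs from it contradicts the protocol.

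**On follow-up, a reader might infer that the 1- and 2-year rates can no longer be estimated, or that they are inflated by a known amount.** The documents support neither. Before Amendment 09, participants were telephoned every 12 weeks for 2 years after EOT. Revised Protocol 07, which added Arm F and Part 2B, is dated 15-Nov-2020 and Amendment 09 14-Mar-2023, which is 849 days apart. Some participants could therefore have passed 2 years under the previous rule. Any bias depends on when accrual ended, on the data cut and on hazards, none of which the documents fix. Under plausible assumptions it is about zero, and it can reverse. A descriptive summary of data already collected is also compatible with the addendum, although the text does not say that this is what is meant.

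**Conclusion.** The origin point holds and is minor. As written, OS in Part 1 and Part 2B includes a death-free interval before first dose and runs on a different clock from PFS and TTR. The direction is certain: OS is longer than it would be from first dose. The size depends on the gap, which is nominally at most 30 days, and on the survival curve. Under the exponential assumption and the borrowed medians, 1-year OS rises by about 1.0 to 3.1 points and 2-year OS by about 0.4 to 1.4 points.

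It would be a mistake to extend this to Part 2A, where OS starts at randomization, or to any primary or secondary conclusion. Table 4-1 has no OS objective for Part 1, so there the point concerns only the table row.

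The follow-up point is secondary: current passages conflict and need reconciling. No magnitude is claimed.

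**What to change.** In Table 10.3.1-1 and the SAP, define OS in Part 1 and Part 2B from the first dosing date, as for PFS and TTR, and leave Part 2A at randomization. The cost is a wording change and slightly shorter reported OS.

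Reconcile Tables 4-2, 4-3 and 10.3.1-1 with the Section 5.1.5.3 addendum, and state an OS censoring rule. Either drop the landmarks that the follow-up does not support, or keep them as descriptive, with numbers at risk and a caveat about informative censoring. Figure 5.1-3, which still shows survival follow-up to 2 years after EOT, should be aligned. The cost is possibly losing a 2-year rate from an exploratory summary.

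One tempting repair needs care. Counting deaths up to a calendar cut while censoring survivors at an earlier last contact biases the Kaplan-Meier estimate downward, because survivors leave the risk set early while deaths in the same interval are still counted. A common calendar cut is sound only if vital status is ascertained to that date for everyone, or if deaths and survivors are handled symmetrically.
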